6. INCLUSION AND EXCLUSION CRITERIA

This is a single arm phase II study designed to determine the effects of pharmacotherapy and a POWER-remote weight loss intervention implemented as part of routine oncology practice, and the impact of successful weight loss on serum biomarkers of obesity that may be used to design future studies.

6.1 Inclusion criteria

6.1.1 Female, at least 3 months after completion of local therapy (e.g. surgery, radiation), and if applicable, adjuvant chemotherapy

NOTE: Concurrent endocrine therapy or anti-HER2 therapy is permitted. Concurrent enrollment in other interventional or drug clinical trials is at the discretion of the Protocol Chair.

- 6.1.2 Diagnosed within 15 years with histologically-confirmed ductal carcinoma in situ (DCIS) or stage I-III invasive carcinoma of the breast
- 6.1.3 Up to date with recommended screening mammography within one year

NOTE: Women who have had a mastectomy (including simple mastectomy, modified radical mastectomy, and radical mastectomy) to treat breast cancer need no further routine screening mammograms on the affected side. If both breasts are removed (a double or bilateral mastectomy), they don't need mammograms at all.

NOTE: Women who have had breast-conserving surgery (e.g., partial mastectomy or lumpectomy) should have a mammogram of the treated breast 6 to 12 months after radiation treatment ends. After that, women should have annual mammograms.

6.1.4 Current BMI \geq 30 kg/m2 or BMI 27.0-29.9 kg/m2 with hypertension, non-insulin dependent diabetes or hyperlipidemia; and weight \leq 400 lbs

NOTE: Participants should not have weight loss greater than 5% of body weight in the last 6 months. All weights for determination of eligibility may be determined by self-report of weight if not documented in the medical records. During the study, if any surgical procedures are required, the difference between weight prior to surgery and after surgery will be accounted for and require notification of the Protocol Chair/designee.

- 6.1.5 Eastern Cooperative Oncology Group (ECOG) performance status 0-1 (Appendix A)
- 6.1.6 Willingness to change diet, physical activity, track behaviors, engage in weekly and monthly contacts and visit, and take chronic weight loss medication
- 6.1.8 Able to read and write the English language without assistance and daily access to the email and/or smartphone

NOTE: Participants who are unable to receive email or to complete the online questionnaires for any reason will not be eligible for the study.

6.1.9 Patient is aware of her diagnosis, understands the study regimen, its requirements, risks, and discomforts, and is able and willing to sign an informed consent form.

6.2 Exclusion criteria

- 6.2.1 Serious/uncontrolled medical condition at the discretion of the Protocol Chair/designee likely to hinder accurate measurement of weight or any condition for which weight loss is contraindicated or would affect adipokine and inflammatory markers (e.g. active malignancy, end stage renal disease on dialysis, cirrhosis, autoimmune disease, adrenal disease, uncontrolled hypertension, seizure disorder, and history of bariatric surgery)
- 6.2.2 Pregnant or nursing within past 6 months, or plans to become pregnant in the next year

- 6.2.3 Currently enrolled or planning to enroll in a weight loss program (e.g. Weight Watchers, Jenny Craig, Nutrisystem and Medifast) or to take a chronic weight loss medication.
- 6.2.4 Diabetes on insulin or sulfonylureas within the past 3 months
- 6.2.5 Unstable psychiatric disorder or bulimia/anorexia nervosa
- 6.2.6 Alcohol, nicotine or substance abuse; or undergoing abrupt discontinuation of alcohol, benzodiazepine, barbiturate or anti-epileptic drug
- 6.2.7 Use of the following medications are excluded:
 - Tamoxifen
 - MAO inhibitors (must be >14 days from discontinuation)
 - Thyroid medication use unless on stable doses for at least the past 3 months
 - Buproprion containing products or opiate agonists (must be >14 days from discontinuation)
 - Medications that cause weight loss (e.g., lorcaserin, phentermine, orlistat, Qsymia, Contrave) within the past 3 months
 - Medications that are likely to cause weight gain or prevent weight loss (e.g., corticosteroids, lithium, olanzapine, risperidone, clozapine, oral contraceptive pills, hormone replacement therapy) within the past 3 months. NOTE: An exception to this is that SSRI's and SNRI's are allowed if participant has been on stable doses for at least 3 months (if discontinued, a washout of 2 weeks from prior SSRI/SNRI use is required).
 - Medications that may affect adipokine or inflammatory markers (e.g., metformin, glitazones, steroids, ACE inhibitors, beta blockers and statins) unless on stable doses ≥3 months prior to registration (if discontinued, a washout of 2 weeks from prior use is required). Concurrent NSAIDs are allowed if use is limited to <3 times per week; chronic NSAIDs are permitted on study only if use has been ≥3 times per week for at least 3 months prior to registration and is expected to continue.

NOTE: No medication should be discontinued without guidance of the prescribing provider.

6.3 Inclusion of women and minorities

Women of all races and ethnic groups are eligible for this trial. There is no bias towards age or race in the clinical trial outlined. This trial is open to enrollment of women only.

7. STUDY DESIGN AND TREATMENT PLAN

7.1 Recruitment

Patients will be recruited through the breast cancer clinics at Johns Hopkins Medical Institute, including the Sidney Kimmel Comprehensive Cancer Center in Baltimore MD and Green Spring Station in Lutherville-Timonium MD, and Sibley Memorial Hospital in Washington D.C. Participants will also be recruited at LHAAMC in Annapolis MD. Study participants will be prescreened by the Johns Hopkins breast cancer survivor registry from 2015-2019. Patients can also be recruited directly through these clinics. We have previously established our ability to

recruit patients with similar characteristics to a POWER-remote study⁴. Additionally, we are including a recruitment letter from the study Protocol Chair and study oncologist to send to clinic patients that we have been unable to reach by phone. We have also uploaded an online screener that will be administered via REDCAP. The purpose of the screener is to aid in visibility of the study and initial assessment of eligibility. We find that giving interested individuals immediate feedback on their initial eligibility helps them remain interested in the study until the coordinator can call them back. Recruitment may be expanded to include eligible breast cancer survivors in the region with flyers.

7.2 Determination of Eligibility

After eligibility is established by the coordinator during the screening call, the study staff will register participants, assign a study number, and schedule an in-person baseline visit. Participants will not begin protocol-specified treatment until eligibility is confirmed by the study staff at the baseline visit. Participants who sign a consent form, but do not initiate protocol intervention for any reason, will be replaced and will not count towards our accrual goal.

7.3 Visits and Follow up

The study will include a 24-month recruitment period, a 6-month implementation period, which involve 3 in-person visits and at least 16 phone sessions for each participant. We anticipate enrolling 2-4 participants per month. All women will receive the POWER remote behavioral weight loss intervention (BWL) and a behavioral coach. They will all receive lifestyle guidelines (See Appendix B). At week 9, those who lose ≥5%, designated fast responders, will continue with BWL alone (FAST-BWL) while those who lose <5%, designated slow responders, will receive BWL with the addition of Contrave (SLOW-BWL).

Women in SLOW-BWL will initiate Contrave one 8-mg naltrexone/90-mg bupropion tablet per day and increased over 3 weeks to the maintenance dosage of two 8-mg/90-mg tablets twice daily, for a total daily dose of 32mg/360mg. It should be taken by mouth in the morning and in the evening and should not be cut, chewed, or crushed. In clinical trials, Contrave was administered with meals. However, it should not be taken with a high-fat meal because of a resulting significant increase in bupropion and naltrexone systemic exposure. As patients are instructed to follow the DASH (Dietary Approaches to Stop Hypertension) and/or Mediterranean diet, this should not be an issue. Patients will be instructed that ketogenic and low carbohydrate diets would impact the absorption of Contrave.

The behavioral coach will review the weekly weight and new symptoms entry (patient will completed in REDCap survey or via telephone if not done) for months 3-6 for participants in both arms. The REDCap survey (Appendix C) asks patients about any new symptoms and includes examples of those which had a frequency of at least 4% in patients on Contrave in clinical trials. Any new symptoms noted will be directed to the Protocol Chair for further evaluation. If patients on Contrave have significant adverse effects, providers will decrease the dose by 50% and assess tolerability over 1 week. If symptoms are alleviated, patient can

continue at lowered dose. If symptoms persist, dose can be lowered by 50% again. If symptoms are alleviated, patient can continue at lowered dose. However, if symptoms persist, the medication should be discontinued and the patient should continue with BWL alone. Following the prescribing information, Contrave will be discontinued for patients who do not achieve \geq 5% and seen in person once a month to assess compliance and potential side effects.

The weight loss intervention is based on the remote-support arm of the POWER trial that was also used by our team in a previous study in breast cancer survivors^{3,4}. It involves two main components: an online portion that participants access on their computer or phone and a telephone/teleconferencing portion to help monitor progress and deliver the behavioral intervention. All participants will receive the POWER intervention, which will be remote and last 6 months. Participants will be given a physical activity monitor (Fitbit) that encourages increased activity by measuring steps and process variables, such as heart rate and sleep. Participants will use a web-based platform to access learning materials and log their diet and exercise each day. They will also record their weight once weekly through our survey. As participants monitor their own progress, they will receive telephone/teleconferencing calls on a regular schedule by a weight loss coach to help monitor and guide progress utilizing dietary, physical activity and weight information. All contacts will be phone/teleconferencing based and last about 30 minutes. For all participants, contacts will occur weekly during the first 3 months (a baseline visit followed by 12 phone sessions) and monthly for the remaining 3 months (3 phone sessions). At the conclusion of the study after 6 months of behavioral intervention, participants will have an in-person visit.

7.3.1 Screening (by phone call)

- Informed consent
- History and physical information will be noted from most recent, standard of care assessment included in the medical records. (NOTE: Participants who may be referred from outside the institution may meet with a medical/clinical member of the study staff at baseline; however, a documented H&P by a study team member is not required.)
- Physical measurements (weight and height) as per patient or chart for BMI calculation
- Review of weight loss history
- Collect current medications and medication history
- Smartphone access and/or access to programs online
- Assess willingness to change diet, physical activity, track behaviors, engage in weekly and monthly contacts and visit, and take chronic weight loss medication (yes/no question format)
- Through REDCap, baseline questionnaire should be completed at home ≤2 weeks prior to baseline visit, but may be completed at baseline visit too. As noted in the eligibility, participants that are unable to complete the questionnaires will not be able to

continue/enroll in the study. NOTE: Patients who complete a screening visit, but who are not eligible, will be offered the "Aim for healthy weight" handout (Appendix D).

7.3.2 Baseline Visit

The Baseline Visit is in-person and should ideally occur within 8 weeks of the screening visit; with baseline questionnaires completed ≤8 weeks prior.

- Written informed consent
- Physical measurements (weight and height) and BMI calculations
- Vital signs (temperature, blood pressure, heart rate, breathing rate, oxygen level)
- Complete medical history and overall general health (performance status)
- If a documented physical exam is not performed within 3 months, this will be performed at or after baseline visit (but before initiation of the behavioral intervention)
- Meet with weight-loss coach
- Receive Fitbit device for monitoring physical activity (participants will wear this on their non-dominant hand for a minimum of 4 of 7 days with 10 hours per day)
- Receive weight scale
- Check heart rate and blood pressure
- Confirm current medications and medication history
- Blood sample (Pregnancy test for < 60 years of age and not taking medication designed to suppress ovarian function. Will advise contraception for these women.)
- Fecal sample
- Orientation to Fitbit website or smartphone platform by coordinator or coach
- Confirm completion of PROs (or complete in clinic, if needed)

IMPORTANT: Eligibility will be confirmed at the baseline visit. Participants with a BMI of \geq 27 at the screening visit, but with a BMI of \leq 27 at the baseline visit will not have maintained eligibility and will be excluded at present. In addition, if there is \geq 2 kg/m² discrepancy between the screening and baseline visits, the Protocol Chair or designee must be consulted to review the discrepancy; this is to determine that the study endpoints will not be affected by fluctuating/changing weight.

7.3.3 Follow-Up Visits

Participants will be asked to attend in-person follow-up visits at 2 months and 6 months.

All Follow-Up Visits are in-person and should ideally occur within 8 weeks of the assessment visit date.

2 months

- Weight and BMI calculations
- Confirm completion of PROs (or complete in clinic, if needed)
- Confirm current medications and medication history
- Blood samples*
- Fecal sample

6 months (End of study)

- Weight and BMI calculations
- Confirm completion of PROs (or complete in clinic, if needed)
- Collect current medications and medication history
- Blood samples*
- Fecal sample

*Blood will be collected while patient is fasting when possible (i.e., 9-12 hours preferred). Will provide patients with juice or bar after labs. Additionally, participants will be asked to be fasting for follow-up visits even in cases when blood samples are not planned to allow for consistency of anthropomorphic data collection.

In participants who discontinue early, the next planned assessments will be completed early whenever possible (e.g., a participant that withdraws at 6 weeks will be asked to complete week 9 assessment; a participant withdraw at 5 months, the end of study assessment). The last visit should be scheduled once the participant has received the full 6 month intervention.

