4.2 Secondary Objectives

- 4.2.1 To compare cardiometabolic biomarkers (HbA1c, IGF 1, fasting glucose, fasting lipids, fasting insulin, adiponectin and leptin levels), microbiome composition, body composition, and PROs at 2 and 6 months to baseline levels among SLOW-BWL who achieve ≥5% weight loss.
- 4.2.2 To compare cardiometabolic biomarkers, microbiome composition, body composition, and PROs at baseline of SLOW-BWL women who achieve ≥5% weight loss versus the SLOW-BWL women who do not achieve 5% weight loss.
- 4.2.3 To compare the moderate to vigorous physical activity (MVPA) and daily steps at 2 and 6 months to baseline levels among SLOW-BWL who achieved ≥5% weight loss vs the SLOW-BWL who did not achieve 5% weight loss.

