7.4 Measurements

7.4.1 Weight: will be measured at each in-person visit, at approximately the same time of day. The weights are obtained at baseline, week 9 and at the end of study. The ideal weight measurement should be obtained within 7 days of completing the 8 weeks and 6 months behavioral intervention. However, to accommodate participants who may not be able to meet within this window, the weight measurement can be obtained within 14 days of these time points. Weight in light indoor clothes without shoes will be recorded by any trained, certified staff using a high-quality digital scale in any of our Johns Hopkins Medical Institute (JHMI) clinics. Duplicate measurements will be made to ensure accuracy. Weight will be measured in pounds for ease of interpretation by the participants and subsequently converted to kilograms for data analysis. Scales will be calibrated per the Sidney Kimmel Comprehensive Cancer Center's (SKCCC) standards. The engineering department or study staff will perform quarterly calibration checks by using standard weights. The weight at SV will be used to determine eligibility. Measurements will be repeated once, if difference between the two measurements is more than 0.1 kg, measurement will be repeated until difference between two measurements is less than 0.1 kg.

7.4.2 Height: to the nearest 0.1 cm will be measured once at any of our JHMI clinics. The participant stands shoeless on a firm, level surface, with her head in the horizontal (Frankfort) plane. Measurements will be repeated once, if difference between the two measurements is more than 1 cm, measurement will be repeated until difference between two measurements is less than 1 cm.

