8. STUDY CALENDAR

D. I	Screening call	Baseline	Follow-Up Visits ##	
Procedure	for eligibility	Visit ##	Week 9	Month 6
Clinical & Physical Assessments:		•	,	,
Consent		X		
Questionnaires		X		
History	X			
Physical exam		$X^{\#}$		
Current medications	X	X		
Performance status		X		
Weight Loss History	X			
Vitals		X	X	X
Up to date screening	X			
mammography within one year	Λ			
BMI Calculation	X*	X	X	X
Anthropomorphic Measurements:				
Height	X*	X		
Weight	X*	X	X	X
Research Correlates:				
Fecal sample		X	X	X
Serum pregnancy test (if age <60)		X		
Lipid panel, Hba1c		X	X	X
Purple research tube		X		
Red/gray research tube		X	X	X
Research Intervention:		•	·	
Patient Reported Outcomes		X	X	X
Provide Fitbit**		X		
Coaching (BWL intervention)***		X	X	X
Provide weight scale		X		

^{*}If greater than 3 months since last documented height and weight in electronic health record, will use patient reported most recent height and weight to determine eligibility based on BMI. However, BMI measured at baseline will serve as first data point.

^{**}Participants will wear the Fitbit on your non-dominant hand for 7 days and a minimum of 4 days with 10 hours per day of wear time.

^{***}Participants will communicate with their coach by phone. The coach will reach out to the participants at the baseline visit, and will provide weekly calls and emails the first 3 months. The last 3 months, participants will receive monthly calls and emails.

[#] Physical exam: may be performed and documented up to 3 months prior to baseline visit by a coinvestigator or provider within the institution. Or physical exam may be performed at or after baseline visit (but before initiation of the behavioral intervention)

Baseline visits should occur within 8 weeks of screening visit. Follow up visits should occur within 8 weeks of assessment date.

NOTE: Additional standard of care tests may be performed at the discretion of the treating investigator as clinically indicated. The schedule should be followed as closely as is realistically possible; however, the schedule may be modified due to problems such as scheduling delays or conflicts (e.g., clinic closure, poor weather conditions, vacations, etc.) with the guidance of the PI/designee, as appropriate, and will not be reportable as a deviation unless the endpoints of the study or subject safety are affected.

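### Fasting is requested at the 2- and 6-month visits but not at baseline, the visit from which every weight and biomarker change is measured

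*Combined protocol and SAP*

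**What the plan says.** Section 7.3.3 (Follow-Up Visits) holds the only fasting instruction. Its footnote is attached to the 2- and 6-month blood samples: "Blood will be collected while patient is fasting when possible", with 9 to 12 hours preferred. It then adds, so that body measurements are taken consistently, that "participants will be asked to be fasting for follow-up visits even in cases when blood samples are not planned". The section defines follow-up visits as those at 2 and 6 months.

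Section 7.3.2 (Baseline Visit) lists "Physical measurements (weight and height) and BMI calculations" and a blood item that begins "Blood sample (Pregnancy test for < 60 years of age and not taking medication designed to suppress ovarian function". Neither carries the footnote or mentions fasting.

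Section 7.4.1 says that weight "will be measured at each in-person visit, at approximately the same time of day", with shoes off, in light clothing and in duplicate. It says nothing about fasting. The Section 8 calendar adds no fasting rule, but notes: "However, BMI measured at baseline will serve as first data point".

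Objective 4.2.1 compares "fasting glucose, fasting lipids, fasting insulin, adiponectin and leptin levels", among other markers, at 2 and 6 months with baseline. Section 13.1 lists the same fasting analytes at baseline, 2 and 6 months, and defines the primary endpoint as a loss of at least 5% from enrollment baseline weight.

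**The concern.** The protocol itself treats fasting as necessary for consistent body measurement, then leaves out the visit that every change refers to. A site that follows the text exactly can record a fed weight and a fed blood sample at baseline, and fasted ones at week 9 and month 6.

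Two things are at stake.

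- **Biomarkers.** Section 3 hypothesises falls in fasting glucose, fasting insulin and triglycerides. A change from fed to fasted goes the same way with no treatment effect. Objective 4.2.1 is a before-after comparison within one group, so no control arm would show the artefact. Section 13.2 does not separate fasted from unfasted samples.
- **Weight.** Food and fluid present in a fed baseline weight later count as weight lost. The same baseline enters both the week-9 split, which decides who starts Contrave, and the month-6 endpoint.

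**Working it through.** **1. Where fasting is mentioned**

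| Section | Visit | Fasting instruction |
|---|---|---|
| 7.3.2 | Baseline | None |
| 7.3.3 | 2 and 6 months | Blood: when possible, 9-12 h preferred. Attendance: requested even without a blood draw |
| 7.4.1 | All weighings | None (time of day, clothing, duplicates) |
| 8 | All | None |
| 9.1.1 | All blood draws | None (names fasting biomarkers; refers to a Lab Manual) |

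**2. The plan's own design figures.** From 13.1: stop if 1 or fewer of 15, succeed if 7 or more of 30, null rate 10.9%, alternative 29%.

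P(pass | p) = Σ over x = 2 to 15 of P[Bin(15, p) = x] × P[Bin(15, p) ≥ 7 − x].

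This gives 0.0378 at p = 0.109 and 0.8006 at p = 0.29. The stated 5% and 80% are reproduced.

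**3. The 5% line with a fed baseline.** If true weight W is recorded as W + d, the true loss needed is 1 − 0.95(1 + d/W). For W = 80-95 kg (assumed), this is 4.4-4.5% at d = 0.5 kg and 3.8-4.0% at d = 1 kg.

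**4. Assumptions for the rest.** The documents give no fed-fasted weight difference, no SD of percentage loss and no share of women unfasted. I assume:

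- a shift δ of 0.5 or 1 percentage point, in every woman, at both later visits;
- normal percentage loss, with SD s9 = 3 at week 9 (range 2.5-4) and s6 = 5 at month 6 (range 4-7);
- correlation ρ = 0.7 (range 0.5-0.85);
- a true SLOW share of 55% (from 13.1).

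**5. Week-9 split.** SLOW share = Φ(Φ⁻¹(0.55) − δ/s9), with Φ⁻¹(0.55) = 0.126.

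- δ = 0.5: Φ(0.126 − 0.167) = 48.4% (47-50% over s9).
- δ = 1: Φ(0.126 − 0.333) = 41.8% (39-45% over s9).

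Of 55 women, centrally, 55 × (0.55 − 0.484) = 3.6 or 55 × (0.55 − 0.418) = 7.3 would be classed FAST only because of the baseline measurement. About 27 or 23 SLOW women would remain, against the planned 30.

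**6. Primary rule, month-6 shift only.** With SLOW membership held fixed, p′ = 1 − Φ(Φ⁻¹(0.891) − δ/5), which is 12.9% or 15.1%. P(pass) is then 8.0% or 15.2%. This leaves out the week-9 effect in step 5.

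**7. Primary rule, both shifts.** Let a = Φ⁻¹(0.55), and choose b so that [Φ(a) − Φ₂(a, b; ρ)] / Φ(a) = 0.109. Then put a′ = a − δ/s9, b′ = b − δ/s6, and p′ = [Φ(a′) − Φ₂(a′, b′; ρ)] / Φ(a′). The number of SLOW women is kept at 30.

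| δ | SLOW rate, central | P(pass), central | P(pass), range |
|---|---|---|---|
| 0 | 10.9% | 3.8% | n/a |
| 0.5 | 11.2% | 4.4% | 1.6-7.5% |
| 1 | 11.5% | 4.9% | 0.6-13.5% |

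The ranges come from 80 combinations per δ (s9 = 2.5, 3, 3.5, 4; s6 = 4, 5, 6, 7; ρ = 0.5, 0.6, 0.7, 0.8, 0.85). In somewhat over a third of them P(pass) is below 3.8%: the women moved to FAST are those nearest 5%, who are the likeliest later successes.

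**8. Smaller unfasted share.** If half the women are unfasted at baseline, the central SLOW share is 51.7% or 48.4%, and P(pass) is 4.0% or 4.2%.

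**The case against.** The strongest reply is that fasting baseline blood was plainly intended. The analytes are named as fasting at all three times, the same lipid and research tubes are drawn each time, and 9.1.1 points to a Lab Manual that is not among the documents. Weighing and blood draw belong to the same visit, so fasting for one would in practice cover the other. Weighing at a similar time of day also limits the contrast, and follow-up fasting is itself only requested.

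Most of this stands as a limit on size. It shows a missing instruction, so a reader should not infer that an unfasted baseline was planned. It does not close the gap: an analyte's name tells a site nothing about preparing the participant, nothing comparable covers baseline weight, and time of day does not fix the fed state.

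A reader might also infer that the gap biases the primary endpoint in favour of success, with a type I error of 8-15%. The documents do not support that. Those figures arise only when SLOW membership is held fixed (step 6), whereas the plan uses the same baseline weight for the week-9 split. With both effects included, the direction is not determined.

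**Conclusion.** The concern holds as an asymmetry in the measurement procedure, and it should be corrected because a baseline taken in the wrong state cannot be repeated. The clearest consequence is for the secondary glucose, insulin and triglyceride comparisons; the documents give no figures from which to size it. The next is the FAST/SLOW split, where an assumed shift of 0.5-1 point in every woman reclassifies roughly 3-9 of 55 (from 55 × 0.05 to 55 × 0.16). For the primary rule the net effect is uncertain: about 4-5% centrally, which stays within the 5% limit, and roughly 1-13% over the assumptions, against 3.8%. All of these shrink with the share of women actually unfasted at baseline. The stated design figures are correct and are not in dispute.

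**What to change.** - **7.3.2 and the Section 8 calendar:** apply the existing 9-12 hour fasting request to the baseline visit, for both weight and blood.
- **Case report form:** record fasting status (yes/no, and hours) at baseline, week 9 and month 6.
- **13.2:** add an analysis of glucose, insulin and lipid changes limited to pairs in which both samples were fasted, alongside the all-sample analysis.

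I would not report the primary endpoint by baseline fasting status: with about 30 SLOW women the groups would be too small to read.

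The cost is one line in 7.3.2 and the calendar, one form field and one sentence in 13.2. Baseline appointments may need a morning slot, and some pairs will drop out of the fasted-pairs analysis.
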